Attachment 2. Protocol JPBM Clinical Laboratory Tests

Clinical Laboratory Tests

Hematology^a: Clinical Chemistry^{a,d}:

Hemoglobin Serum Concentrations of:

Hematocrit Sodium

Erythrocyte count (RBC) Potassium

Mean cell volume (MCV) Total Protein

Mean cell hemoglobin concentration (MCHC)

Total bilirubin

Leukocytes (WBC) Direct bilirubin

Neutrophils, (segmented and bands)

Alkaline phosphatase

Lymphocytes Alanine aminotransferase (ALT)

Monocytes Aspartate aminotransferase (AST)

Eosinophils Blood urea nitrogen (BUN)

Basophils Creatinine

Platelets Calcium

Albumin

Follicle Stimulating Hormone (FSH) level^{b,c}

Estradiol level^{b,c}

Abbreviations: RBC = red blood cells; WBC = white blood cells.

- a Assayed by Lilly-designated (central) laboratory.
- b Local or investigator-designated laboratory.
- To be performed at baseline in order to establish eligibility only for women <60 years and ammenorrheic for at least 12 months.
- d Per the letrozole and anastrozole labels, investigators should consider monitoring cholesterol. The decision to monitor and frequency of monitoring are at the discretion of the investigator.

Attachment 3. Protocol JPBM Hepatic Monitoring Tests for Treatment-Emergent Abnormality

Selected tests may be obtained in the event of a treatment-emergent hepatic abnormality and may be required in follow up with patients in consultation with the Lilly clinical research physician.

Hepatic Monitoring Tests

Hepatic Hematologya	Haptoglobin ^a
Hemoglobin	
Hematocrit	Hepatic Coagulation ^a
RBC	Prothrombin Time
WBC	Prothrombin Time, INR
Neutrophils, segmented and bands	
Lymphocytes	Hepatic Serologies ^{a,b}
Monocytes	Hepatitis A antibody, total
Eosinophils	Hepatitis A antibody, IgM
Basophils	Hepatitis B surface antigen
Platelets	Hepatitis B surface antibody
* \	Hepatitis B Core antibody
Hepatic Chemistry ^a	Hepatitis C antibody
Total bilirubin	Hepatitis E antibody, IgG
Direct bilirubin	Hepatitis E antibody, IgM
Alkaline phosphatase	
ALT	Anti-nuclear antibodya
AST	
GGT	Anti-smooth muscle antibodya
СРК	

Abbreviations: ALT = alanine aminotransferase; AST = aspartate aminotransferase; CPK = creatine phosphokinase; GGT = gamma glutamyl transferase; Ig = immunoglobulin; INR = international normalized ratio; RBC = red blood cells; WBC = white blood cells.

a Assayed by Lilly-designated laboratory.

b Reflex/confirmation dependent on regulatory requirements and/or testing availability.

Attachment 4. Protocol JPBM ECOG Performance Status

ECOG Performance Status

Activity Status	Description
0	Fully active, able to carry on all pre-disease performance without restriction
1	Restricted in physically strenuous activity but ambulatory and able to carry out work of a light or sedentary nature, e.g., light house work, office work
2	Ambulatory and capable of all selfcare but unable to
	carry out any work activities. Up and about more than 50% of waking hours
3	Capable of only limited selfcare, confined to bed or chair more than 50% of waking hours
4	Completely disabled. Cannot carry on any selfcare. Totally confined to bed or chair
5	Dead.

Abbreviation: ECOG = Eastern Cooperative Oncology Group.

Source: Oken et al. 1982.

Attachment 5. Protocol JPBM RECIST Criteria 1.1

Response and progression will be evaluated in this study using the international criteria proposed by the New Response Evaluation Criteria in Solid Tumors (RECIST): Revised RECIST Guideline (version 1.1; Eisenhauer et al. 2009).

Measurability of Tumor at Baseline

Tumor lesions/lymph nodes will be categorized at baseline as measurable or nonmeasurable. Measurable disease is defined by the presence of at least 1 measurable lesion.

Measurable

Tumor lesions: Measured in at least 1 dimension (longest diameter in the plane of measurement is to be recorded) with a minimum size of:

- 10 mm by computed tomography (CT) or magnetic resonance imaging (MRI) scan (slice thickness ≤5 mm)
- 10 mm caliper measurement by clinical exam (non-measurable lesions if cannot be accurately measured with calipers)
- 20 mm by chest x-ray.

Malignant lymph nodes: To be considered pathologically enlarged and measurable, a lymph node must be ≥ 15 mm in short axis when assessed by CT scan (CT scan thickness recommended to be ≤ 5 mm).

Nonmeasurable

All other lesions, including small lesions (longest diameter <10 mm or pathological lymph nodes with ≥10 to <15 mm short axis) as well as truly nonmeasurable lesions. Lesions considered truly non-measurable include: leptomeningeal disease, ascites, pleural/pericardial effusions, lymphangitis cutis/pulmonis, inflammatory breast disease, lymphangitis involvement of skin or lung, abdominal masses/abdominal organomegaly identified by physical exam that is not measureable by reproducible imaging techniques.

Special Considerations for Lesion Measurability

Bone lesions:

- Bone scan, PET scan or plain films are not considered adequate imaging techniques to measure bone lesions.
- Lytic bone lesions or mixed lytic-blastic lesions, with identifiable soft tissue components, that can be evaluated by cross sectional imaging techniques such as CT or MRI, can be considered measurable lesions if the soft tissue component meets the definition of measurability.
- Blastic bone lesions are non-measurable.

Cystic lesions:

- Simple cysts should not be considered as malignant lesions (neither measurable nor nonmeasurable)
- Cystic lesions thought to represent cystic metastases can be considered as measurable lesions, if they meet the definition of measurability. If noncystic lesions are presented in the same patients, these are preferred for selection as target lesions.

Lesions with Prior Local Treatment:

 Tumor lesions situated at a previously irradiated area, or in an area subjected to other loco-regional therapy, are non-measurable unless there has been demonstrated progression in the lesion.

Baseline Documentation of Target and Non-Target Lesion

Target Lesions

When more than 1 measurable lesion is present at baseline, all lesions up to a maximum of 5 lesions total (and a maximum of 2 lesions per organ) representative of all involved organs should be identified as target lesions and will be recorded and measured at baseline. Non-nodal Target lesions should be selected on the basis of their size (lesions with the longest diameter), be representative of all involved organs, and can be reproduced in repeated measurements.. Measurable lymph nodes are target lesions if they meet the criteria of a short axis of ≥ 15 mm by CT scan. All measurements are to be recorded in the case record form (CRF) in millimeters (or decimal fractions of centimeters [cm]).

Nontarget Lesions

All other lesions (or sites of disease) are identified as nontarget lesions (chosen based on their representativeness of involved organs and the ability to be reproduced in repeated measurements) and should be recorded at baseline. Measurement of these lesions are not required but should be followed as 'present,' 'absent,' or in rare cases 'unequivocal progression.' In addition, it is possible to record multiple nontarget lesions involving the same organ as a single item on the CRF (for example, multiple liver metastases recorded as 1 liver lesion).

Lymph nodes with short axis ≥ 10 mm but < 15 mm should be considered nontarget lesions. Nodes that have a short axis < 10 mm are considered nonpathological and are not recorded or followed.

Specifications by Methods of Measurement

All measurements should be recorded in metric notation, using a ruler or calipers if clinically assessed. All baseline evaluations should be performed as closely as possible to the beginning of treatment and never more than 4 weeks before the beginning of the treatment.

The same method of assessment and the same technique should be used to characterize each identified and reported lesion at baseline and during follow-up. Imaging-based evaluation is

should always be done rather than clinical examination unless the lesion(s) being followed cannot be imaged but are assessed by clinical exam.

An adequate volume of a suitable contrast agent should be given so that the metastases are demonstrated to best effect and a consistent method is used on subsequent examinations for any given patient. If prior to enrollment it is known a patient is not able to undergo CT scans with IV contrast due to allergy or renal insufficiency, the decision as to whether a non-contrast CT or MRI (with or without IV contrast) should be used to evaluate the patient at baseline and follow-up should be guided by the tumor type under investigation and the anatomic location of the disease.

Clinical Lesions: Clinical lesions will only be considered measurable when they are superficial and ≥10 mm diameter as assessed using calipers (for example, skin nodules). For the case of skin lesions, documentation by color photography, including a ruler to estimate the size of the lesion is recommended. When lesions can be evaluated by both clinical exam and imaging, imaging evaluation should be undertaken since it is more objective and may be reviewed at the end of the study.

Chest X-Ray: Chest CT is preferred over chest x-ray when progression is an important endpoint. Lesions on chest x-ray may be considered measurable if they are clearly defined and surrounded by aerated lung.

CT and MRI: CT scan is the best currently available and reproducible method to measure lesions selected for response assessment. Measurability of lesions on CT scan is based on the assumption that CT slice thickness is ≤5 mm. When CT scan have slice thickness >5 mm, the minimum size for a measurable lesion should be twice the slice thickness. MRI is also acceptable in certain situations (for example, for body scans). If there is concern about radiation exposure at CT, MRI may be used instead of CT in selected instances.

Ultrasound: Ultrasound should not be used to measure lesion size. Ultrasound examinations cannot be reproduced in their entirety for independent review at a later date and, because they are operator dependent, it cannot be guaranteed that the same technique and measurements will be taken from one assessment to the next. If new lesions are identified by ultrasound in the course of the study, confirmation by CT or MRI is advised.

Endoscopy, Laparoscopy: The utilization of these techniques for objective tumor evaluation is not advised. However, such techniques can be useful to confirm complete pathological response when biopsies are obtained or to determine relapse in trials where recurrence following complete response or surgical resection is an endpoint.

Tumor Markers: Tumor markers alone cannot be used to assess tumor response. If markers are initially above the upper normal limit, they must normalize for a patient to be considered in complete response (CR). Specific guidelines for both prostate-specific antigen (PSA) response (in recurrent prostate cancer) and CA-125 response (in recurrent ovarian cancer) have been published.

Cytology, Histology: These techniques can be used to differentiate between partial responses (PR) and complete response (CR) in rare cases if required by protocol (for example, residual lesions in tumor types such as germ cell tumors, where known residual benign tumors can remain). When effusions are known to be a potential adverse effect of treatment (for example, with certain taxane compounds or angiogenesis inhibitors), the cytological confirmation of the neoplastic origin of any effusion that appears or worsens during treatment can be considered if the measurable tumor has met criteria for response or stable disease (SD) in order to differentiate between response (or SD) and progressive disease (PD).

Pet Scan (FDG-PET, PET CT): PET is not recommended for lesion assessment. If a new lesion is found by PET, another assessment must be done by CT, unless the PET CT is of diagnostic quality. If CT is done to confirm the results of the earlier PET scan, the date of progression must be reported as the earlier date of the PET scan.

Bone Scan: If lesions measured by bone scan are reported at baseline, it is necessary to repeat the bone scan when trying to identify a complete response (CR) or partial response (PR) in target disease or when progression in bone is suspected.

Response Criteria

Evaluation of Target Lesions

Complete Response (CR): Disappearance of all target lesions. Any pathological lymph nodes (whether target or non-target) must have reduction in short axis to <10 mm. Tumor marker results must have normalized.

Partial Response (PR): At least a 30% decrease in the sum of diameter of target lesions, taking as reference the baseline sum diameters.

Progressive Disease (PD): At least a 20% increase in the sum of the diameters of target lesions, taking as reference the smallest sum on study (including the baseline sum if that is the smallest). In addition to the relative increase of 20%, the sum must also demonstrate an absolute increase of at least 5 mm. The appearance of 1 or more new lesions is also considered progression.

For equivocal findings of progression (for example, very small and uncertain new lesions; cystic changes or necrosis in existing lesions), treatment may continue until the next scheduled assessment. If at the next scheduled assessment, progression is confirmed, the date of progression should be the earlier date when progression was suspected.

Stable Disease (SD): Neither sufficient shrinkage to qualify for PR nor sufficient increase to qualify for PD, taking as reference the smallest sum diameters while on study.

Not Evaluable: When an incomplete radiologic assessment of target lesions is performed or there is a change in the method of measurement from baseline that impacts the ability to make a reliable evaluation of response.

Evaluation of Nontarget Lesions

Complete Response: Disappearance of all nontarget lesions and normalization of tumor marker level. All lymph nodes must be non-pathological or normal in size (<10mm short axis).

Non-CR/ non-PD: Persistence of 1 or more nontarget lesions and/or maintenance of tumor marker level above the normal limits.

Progressive Disease: Unequivocal progression of existing nontarget lesions. The appearance of 1 or more new lesions is also considered progression.

Not Evaluable: When a change in method of measurement from baseline occurs and impacts the ability to make a reliable evaluation of response.

Evaluation of Best Overall Response

The best overall response is the best response recorded from the start of the study treatment until the earliest of objective progression or start of new anticancer therapy, taking into account any requirement for confirmation. The patient's best overall response assignment will depend on the findings of both target and nontarget disease and will also take into consideration the appearance of new lesions. The Best Overall Response will be calculated via an algorithm using the assessment responses provided by the investigator over the course of the trial.

Time Point Response

It is assumed that at each protocol-specified time point, a response assessment occurs. (When no imaging/measurement is done at all at a particular time point, the patient is not evaluable (NE) at that time point.) Table 1 provides a summary of the overall response status calculation at each time point for patients who have *measurable disease* at baseline.

Table 1. Time Point Response: Patients with Target (± Nontarget) Disease

Target Lesions	Non-Target Lesions	New Lesions	Overall Response
CR	CR	No	CR
CR	Non-CR/non-PD	No	PR
CR	Not evaluated	No	PR
PR	Non-PD or not all evaluated	No	PR
SD	Non-PD or not all evaluated	No	SD
Not all evaluated	Non-PD	No	NE
PD	Any	Yes or No	PD
Any	PD	Yes or No	PD
Any	Any	Yes	PD

Abbreviations: CR = complete response; PR = partial response; SD = stable disease.; PD = progressive disease; NE = inevaluable.

Table 2 is to be used when patients have *nonmeasurable* disease only.

Nontarget Lesions	New Lesions	Overall Response
CR	No	CR
Non-CR/non-PD	No	Non-CR/non-PD ^a
Not all evaluated	No	NE
Unequivocal PD	Yes or No	PD
Any	Yes	PD

Table 2. Time Point Response: Patients with Nontarget Disease Only

Abbreviations: CR = complete response; PD = progressive disease; NE = inevaluable.

Frequency of Tumor Re-Evaluation

A baseline tumor evaluation must be performed within 4 weeks before patient begins study treatment. Frequency of tumor re-evaluation while on and adapted to treatment should be protocol-specific and adapted to the type and schedule of treatment. In the context of Phase 2 studies where the beneficial effect therapy is not known, follow-up every 6-8 weeks is reasonable. Normally, all target and non-target sites are evaluated at each assessment using the same method. However, bone scans may need to be repeated only when CR is identified in target disease or when progression in bone is suspected.

Confirmatory Measurement/Duration of Response

Confirmation:

The main goal of confirmation of objective response in clinical trials is to avoid overestimating the response rate observed. The confirmation of response is particularly important in *nonrandomized trials* where response (CR/PR) is the primary end point. In this setting, to be assigned a status of PR/CR, changes in tumor measurements must be confirmed by repeat assessments that should be performed no less than 4 weeks after the criteria for response are first met. To confirm a response of CR, a full assessment of all target and nontarget lesions that were present at baseline must occur, including those measured by bone scan. To confirm a PR or SD, a full assessment of target lesions that were present at baseline must occur; assessment of nontargets is not required.

However, in *randomized trial* (Phase 2 or 3) or studies where SD or progression is the primary endpoints, confirmation of response is not required. But, elimination of the requirement may increase the importance of central review to protect against bias, in particular of studies which are not blinded.

In the case of SD, follow-up measurements must have met the SD criteria at least once after start of treatment at a minimum interval not less than 6 weeks measured from randomization.

^a non-CR/non-PD is preferred over SD for nontarget disease.

Duration of Overall Response

The duration of overall response is measured from the time measurement criteria are first met for CR or PR (whichever is first recorded) until the first date that disease is recurrent or objective progression is observed (taking as reference for PD the smallest measurements recorded on study).

The duration of overall CR is measured from the time measurement criteria are first met for CR until the first date that recurrent disease is objectively documented.

Duration of Stable Disease

Stable disease is measured from the start of the treatment (in randomized trials, from date of randomization) until the criteria for objective progression are met, taking as reference the smallest sum on study (if the baseline sum is the smallest, that is the reference for calculation of PD).

Independent Review of Response and Progression

When objective response (CR + PR) is the primary end point, and when key drug development decisions are based on the observation of a minimum number of responders, it is recommended that all claimed responses be reviewed by an expert(s) independent of the study. If the study is a randomized trial, ideally reviewers should be blinded to treatment assignment.

Attachment 6. Protocol JPBM Sampling Summary

This table summarizes the purpose for sampling, sample types, maximum volume per sample, maximum number of samples, and maximum total volume during the study. The summary below provides estimates. More samples could be required in the case of retests, additional health monitoring (if needed), or for patients continuing treatment beyond the protocol-specified number of cycles in the study. Fewer samples may actually be taken (for example, patients who discontinue from the study).

Protocol I3Y-MC-JPBM Sampling Summary^a

Purpose	Sample Type	Maximum Amount per Sample	Maximum Number Samples	Maximum Total Amount
Screening/Study qualification (Hematology and Clinical Chemistry)	Blood	7 mL	l	7 mL
Safety/Health monitoring (Hematology and Clinical Chemistry)	Blood	7 mL	17	119 mL
Pharmacokinetic sample	Blood	4 mL	5	20 mL
Pharmacogenetic blood sample	Blood	10 mL	1	10 mL
Biomarker plasma sample	Blood	6 mL	3	18 mL
Total blood volume	Blood			174 mL
Hepatic monitoring ^b	Blood	3 - 30 mL	-	-

a Covers Cycles 1 through 16 and one post-discontinuation follow up visit.

b Based on laboratory safety values, unscheduled hepatic monitoring testing may be performed as part of patient follow-up, in consultation with the designated medical monitor.

Attachment 7. Protocol JPBM Electrocardiogram and Pharmacokinetic Sampling Schedule

The schedule for PK sampling is summarized in the table below. The date and exact time of collection for each venous blood sample should be documented on the laboratory requisition.

Pharmacokinetic Sampling Schedule

Cycle(C) and Day(D)	ECG	PK Sample Number	Study Drug Dose	Dosing of anastrozole / letrozole	Sampling Time for ECG and PK from Blood ^a
Baseline (Day -14 to Day -1)	X				Day of visit
C1D1	X	1	X ^b	X^{b}	2-4hrs after NSAI and blinded study drug dosed in clinic
C2D1	X	2	Xc	X°	Upon arrival at site (that is, at least 4 hrs after taking NSAI and blinded study drug doses at home)
C2D1		3			3±0.5 hrs after arrival at site (that is, at least 7±0.5 hrs after taking NSAI and blinded study drug doses at home.
C3D1		4	Xp	X^{b}	Prior to NSAI and blinded study drug doses. Patient is dosed in clinic after sample collection.
C3D1		5			3±0.5hrs after NSAI and blinded study drug dosing in clinic
C4D1	Х		Xb	X ^b	2-4hrs after NSAI and blinded study drug dosing in clinic.
30 Day Follow-Up	X				Day of visit

Abbreviation: hrs = hours; NSAI = nonsteroidal aromatase inhibitor; PK = pharmacokinetic.

- ^a Samples of approximately 4 mL of whole blood will be drawn from at least 150 patients randomized in the study for measurement of study treatment and LY2835219 metabolites concentrations.
- Patient is administered NSAI and study drug doses in clinic. On Cycle 1 Day 1 only, patients should take one single dose of blinded study drug and initiate chronic every 12 hours dosing on Cycle 1 Day 2
- c Patient should take NSAI and study drug doses at home at least 4 hours before arrival at site. The time of NSAI and study drug dose intake must be recorded that day..

Attachment 8. Protocol JPBM Inducers and Strong Inhibitors of CYP3A4

The information in this attachment is provided for guidance to investigators and does not preclude the use of these medications if clinically indicated.

Inducers of CYP3A4

Carbamazepine

Dexamethasone^a

Phenobarbital/phenobarbitone

Phenytoin

Rifapentine

Rifampin

Rifabutin

St. John's wort

Strong inhibitors of CYP3A4

All HIV protease inhibitors

Clarithromycin

Itraconazole

Ketoconazole

Nefazodone

^a Important note: All patients may receive supportive therapy with dexamethasone, preferably ≤7 days, if clinically indicated. Patients requiring more than 7 days of dexamethasone therapy will not incur a protocol deviation.

Attachment 9. Protocol JPBM CTCAE 4.03 Diarrhea Definition

Diarrhea will be evaluated in this study using the criteria proposed by Common Terminology Criteria for Adverse Events (CTCAE) v4.0 revised: CTCAE 4.03-June 14, 2010: Gastrointestinal disorders.

Gastrointestinal Disorders									
Grade									
Adverse Event	1	2	3	4	5				
Diarrhea	Increase of <4 stools per day over baseline; mild increase in ostomy output compared to baseline.	Increase of 4-6 stools per day over baseline; moderate increase in ostomy output compared to baseline	Increase <= 7 stools per day over baseline; incontinence; hospitalization indicated; severe increase in ostomy output compared to baseline; limiting self-care ADL	Life-threatening consequences; urgent intervention indicated	Death				
Definition: a disorder characterized by frequent and watery bowel movements									

Abbreviation: ADL = Activities of Daily Living.

Leo Document ID = 6d4002b3-1936-489c-96a3-ae1f8e416e2a

Approver:
Approval Date & Time: 03-Sep-2014 15:11:41 GMT
Signature meaning: Approved

Approver: Approval Date & Time: 03-Sep-2014 23:57:08 GMT

Signature meaning: Approved

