9.4.1.1.4. Nonhematological Toxicity

If a patient experiences ≥Grade 3 nonhematologic toxicity, then blinded study drug and/or NSAI dosing must be suspended (until the toxicity resolves to either baseline or at least Grade 1) and the dose of blinded study drug must be reduced by one dose level as outlined in Table JPBM.9.2.

If a patient experiences persistent or recurrent Grade 2 nonhematologic toxicity (except diarrhea; refer to Section 9.4.1.1.4.1) that does not resolve with maximal supportive measures within 7 days to either baseline or at least Grade 1, then blinded study drug and/or NSAI dosing may be suspended (until the toxicity resolves to either baseline or at least Grade 1) and the dose of blinded study drug may be reduced by one dose level as outlined in Table JPBM.9.2 at the discretion of the investigator.

Before the start of each cycle, nonhematologic toxicity (except alopecia and fatigue) must resolve to either baseline or at least Grade 1.

9.4.1.1.4.1. Diarrhea

A patient experiencing diarrhea requiring hospitalization (irrespective of grade, that is, requiring intravenous [IV] rehydration) or severe diarrhea (Grade 3 or 4; see Attachment 9) must have study treatment suspended (until the toxicity resolves to either baseline or at least Grade 1) and must have the blinded study drug dose reduced by one dose level as outlined in Table JPBM.9.2.

If a patient experiences persistent or recurrent Grade 2 diarrhea that does not resolve with maximal supportive measures (refer to Section 9.6.5) within 3 days to either baseline or at least Grade 1, then study treatment should be suspended (until the toxicity resolves to either baseline or at least Grade 1) and the dose of blinded study drug may be reduced by one dose level as outlined in Table JPBM.9.2 at the discretion of the investigator. If the same dose level was resumed and diarrhea recurs despite maximal supportive measures, the dose of blinded study drug must be reduced by one dose level as outlined in Table JPBM.9.2.

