9.6.5. Supportive Management for Diarrhea

In the event of diarrhea, supportive measures should be initiated as early as possible. These include the following:

- At the first sign of loose stools, the patient should initiate anti-diarrheal therapy (e.g. loperamide) and notify the investigator for further instructions and appropriate follow-up.
- Site personnel should assess response within 1 to 3 days.
- If diarrhea does not resolve with anti-diarrheal therapy within 3 days to either baseline or Grade 1, then dosing should be adjusted as outlined in Section 9.4.1.1.1.1 and Table JPBM.9.2.
- Patients should also be encouraged to drink fluids (e.g., 8 to 10 glasses of clear liquids per day).

In potentially severe cases of diarrhea, the measuring of neutrophil counts and body temperature and proactive management of diarrhea with antidiarrheal agents should be considered.

If diarrhea is severe (requiring IV rehydration) and/or associated with fever or severe (Grade 3 or 4) neutropenia, broad-spectrum antibiotics such as fluoroquinolones must be prescribed.

Patients with severe diarrhea or any diarrhea associated with severe nausea or vomiting should be carefully monitored and given fluid (IV hydration) and electrolyte replacement.

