The National Cancer Institute (NCI)-CTCAE v 4.0 will serve as the reference document for choosing appropriate terminology for, and grading the severity of, all AEs and other symptoms. For AEs without matching terminology within the NCI-CTCAE v 4.0 criteria, the investigator will be responsible for selecting the appropriate system organ class and assessing severity grade based on the intensity of the event.

In addition to collecting the AE verbatim and the CTCAE severity grade, AE verbatim text will also be mapped by Lilly or its designee to corresponding terminology within the Medical Dictionary for Regulatory Activities (MedDRA) dictionary.

If a patient's dosage is reduced or treatment is discontinued as a result of an AE, study site personnel must clearly report to Lilly or its designee via eCRF the circumstances and data leading to any such dosage reduction or discontinuation of treatment.

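### Protocol Attachment 9, as supplied, prints the Grade 3 diarrhea stool count with the sign reversed (≤ 7 instead of ≥ 7), in the table cited for a mandatory dose action; a minor correction

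*Protocol*

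**What the plan says.** Attachment 9 presents itself as the CTCAE 4.03 definition of diarrhea. Its cells give:

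- Grade 1: "Increase of <4 stools per day over baseline; mild increase in ostomy output".
- Grade 2: "Increase of 4-6 stools per day over baseline", or a moderate rise in ostomy output.
- Grade 3: "Increase <= 7 stools per day over baseline; incontinence; hospitalization indicated", or a severe rise in ostomy output, or limited self-care.
- Grade 4: life-threatening consequences, with no stool count.

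Protocol Section 9.4.1.1.4.1 uses the table in a dosing rule. Its first paragraph covers "diarrhea requiring hospitalization (irrespective of grade, that is, requiring" intravenous rehydration) and also "severe diarrhea (Grade 3 or 4; see Attachment 9"). In either case study treatment must be suspended and blinded drug must be reduced by one level.

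The Grade 2 rule in the same section is softer. It applies to persistent or recurrent diarrhea that has not settled within 3 days on full supportive measures. Treatment should then be suspended, and "the dose of blinded study drug may be reduced by one dose level as outlined in Table JPBM.9.2 at the discretion of the investigator". Reduction becomes mandatory only if the same dose was resumed and the diarrhea returns.

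**The concern.** Severity grades should be ordered and should not overlap. A Grade 3 cell bounded above by 7 takes in all of Grades 1 and 2 and excludes the highest counts. The Grade 2/3 line decides whether action is immediate or waits 3 days, and whether a first reduction is required or optional.

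Diarrhea is also a toxicity this protocol singles out. Section 5 reports treatment-emergent Grade 3 diarrhea at the 200 mg dose of 25.7% with NSAI against 13.6% for the drug alone, and cites the preliminary safety data from that combination study in support of 150 mg. A grading table included to guide dosing for this toxicity should be correct.

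Two errors are possible at a site that grades from the attachment alone. Mild or moderate diarrhea could be treated as severe, with an unneeded interruption and dose reduction. A large increase in stools, with none of the other Grade 3 features, could be left without a grade.

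**Working it through.** No sample size, power or alpha figure is involved. The check applies the three count criteria in Attachment 9 to each whole-number increase from 1 to 12 stools per day, first as printed and then with the Grade 3 sign reversed. Grade 4 has no count and drops out.

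Criteria for an increase x: Grade 1 if x < 4; Grade 2 if 4 ≤ x ≤ 6; Grade 3 if x ≤ 7 (as printed) or x ≥ 7 (reversed).

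| Increase per day | Grades met as printed | Grades met with ≥ 7 |
|---|---|---|
| 1, 2, 3 | 1 and 3 | 1 |
| 4, 5, 6 | 2 and 3 | 2 |
| 7 | 3 | 3 |
| 8 to 12 | none | 3 |

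The rows for 8 to 12 extend to every higher value, because no printed count criterion reaches above 7.

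For the mandatory rule, by count alone and read literally:

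- 3 + 3 = 6 values (1 to 6) meet the suspend-and-reduce criterion when they should not.
- 1 value (7) is unchanged.
- Every value of 8 or more loses its count-based trigger.

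With ≥ 7 there is no overlap and no gap. The direction of the sign follows from the row itself: Grade 2 stops at 6 and the next number is 7. No outside source is needed.

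The next step is to ask which other provisions still act if the cell is wrong.

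1. **Grading standard.** Protocol Section 10.3.1 says that NCI-CTCAE v4.0 "will serve as the reference document for choosing appropriate terminology for, and grading the severity of, all AEs". SAP Section 6.11.2 also has investigators grade by CTCAE Version 4. A site that follows the standard is not misled in either direction.
2. **Other Grade 3 criteria.** Incontinence, an indication for hospitalization, severe ostomy output and limited self-care do not depend on the count.
3. **Hospitalization.** It triggers the mandatory action at any grade.
4. **Section 9.6.5.** "If diarrhea does not resolve with anti-diarrheal therapy within 3 days to either baseline or Grade 1, then dosing should be adjusted". An unresolved increase of 8 or more is neither baseline nor Grade 1, so this reaches it after 3 days.
5. **Section 9.4.1.1.4.** Directly above the diarrhea rule, it requires suspension of blinded drug and/or NSAI and a one-level reduction of blinded drug for any nonhematologic toxicity of Grade 3 or higher. It does not cite Attachment 9. Diarrhea is carved out only in its Grade 2 paragraph.

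Item 5 matters most for increases of 8 or more: once such an event is graded 3 under CTCAE, suspension and reduction are mandatory whatever the attachment prints. It differs slightly from the diarrhea rule, which suspends study treatment rather than blinded drug and/or NSAI. Items 2 to 5 do not prevent over-triggering at increases of 1 to 6; only item 1 does.

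**The case against.** The strongest objection is that the point rests on one sign in a table that was extracted from a PDF by a program. The protocol text shows character damage elsewhere, including in the dosing markers of Attachment 7 and the dose line of Section 9.1, and comparison signs are rendered inconsistently. This stands as a limit. On the other side, the rest of the row is clean, and the cell has a two-character sign where similar signs elsewhere, such as in Attachment 8, came through as a single character. Typing is at least as likely as misreading, but the documents cannot settle it.

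The second objection is currency. The supplied protocol was approved on 03-Sep-2014. The SAP, approved on 14-Apr-2017, refers in Sections 3 and 8 to protocol amendments (a) and (b), which were not supplied. The cell may already have been corrected. This also stands.

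The third objection is that the attachment only restates a named standard and that any clinician would see the intended meaning. That explains why the effect is small. It does not cure the cell, because the dosing rule cites the attachment and the attachment claims to be the CTCAE definition.

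A reader might infer that a patient with 8 or more extra stools per day would escape mandatory action. Section 9.4.1.1.4, applied with CTCAE grades, does not allow that reading. A reader might also infer that patients were misgraded or wrongly dose-reduced, or that the Grade 3 diarrhea rates are unreliable. Nothing in the documents shows a misgraded event or how many events rest on stool count alone, and the counts of whole-number values above are not an expected rate of error.

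**Conclusion.** The point holds as a minor correction, conditional on the sign being confirmed. As supplied, the Grade 3 stool-count threshold contradicts the two cells beside it, in the table sites are told to use for a mandatory dose action.

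What remains after the other provisions is that internal contradiction, with possible over-triggering at increases of 1 to 6 and possible under-grading at 8 or more, limited to a site that grades from the attachment alone. The size of that effect cannot be estimated from the documents, and there is no reason in them to think it large. Sample size, power, type I error and the planned analyses do not depend on this cell.

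The conclusion assumes that the sign is printed as extracted and that neither amendment has changed it.

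**What to change.** Check the sign on the original page of Attachment 9 and in protocol amendments (a) and (b). If it stands, change the Grade 3 cell to an increase of ≥ 7 stools per day over baseline, leave the other Grade 3 criteria as they are, and send sites a short note. The cost is one page check, a look at two amendments and, if needed, a one-cell correction. No retrospective review of events is proposed, since nothing in the documents points to misgrading.
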